- 3. Mitochondrial respiratory demand relative to intramyofiber statin concentration. Our preliminary data indicate that statin-induced inhibition of respiration increases as a function of ADP-

- stimulated respiratory demand (Fig. 3 & 4). In other words, inhibition is negligible at low rates of respiration, but is clearly present as the demand for respiration increases. This could explain why exercise increases the risk of developing myopathic symptoms (23, 55) and why statins are not well tolerated by athletes (56).
- 4. Declining respiratory reserve capacity over time. Recent reports indicate patients may not present with myopathic symptoms until several years after initiating statin treatment (25). A slowly progressing decline in mitochondrial content as a result of aging and/or inactivity will decrease the density of mitochondria over which the statin is distributed (#1) and increase the relative respiratory demand on the remaining mitochondria (#3). This reduces the available reserve capacity, eventually reaching the point (i.e., threshold) where the decline in function imposed by the statin creates added demand to existing mitochondria that exceeds the reserve capacity and is sufficient to generate myopathic symptoms.

In summary, the goal is to determine if atorvastatin therapy induces a progressive decline in skeletal muscle mitochondrial respiratory function, insulin sensitivity, and cardiorespiratory fitness that is dose and duration dependent.

II. Research Plan and Design

A. Study Objectives: The overall aim of the study is to determine the impact of low and high dose statin therapy on skeletal muscle mitochondrial function, insulin sensitivity, and cardiorespiratory fitness.

a. Primary Objective:

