- C. Sample size, statistical methods, and power calculation: The randomization for study drugs will be carried out by the biostatistician using a computer-based random number generator at a 1:1:1 allocation. Sample size for study is powered on the basis of detecting a difference in mitochondrial respiratory function, the primary outcome measure, between three groups (e.g., placebo, and 20 or 80 mg/d atorvastatin therapy) at 12 months posttreatment. Our pilot study of statin effect on maximal ADP-stimulated O2 consumption rate (JO_2) after 56 days based on 8 participants showed a mean change of 88.5 (pmol/sec/mg) with standard deviation of 59.9 (pmol/sec/mg), which can be standardized into a very large pre-post effect size of -1.48 (Cohen's d). All of these 8 participants experienced a decrease of 11.13% to 66.94% in 56 days, suggesting the decreasing trends are very consistent among participants. The overall decreasing trend of maximal ADP-stimulated O2 consumption rate across all time points also suggests that the decreasing trend will continue beyond 56 days. For the other outcomes variables, insulin-sensitivity and in-vivo O2 recovery kinetics (NIRS), only measurements at baseline and day 56 are available and the observed changes are -0.65 (1.20) (mU/L)⁻¹ min⁻¹ and 19.07 (21.80) mVO₂, which can be standardized into effect sizes of -0.54, and 0.87, respectively. In a much longer study period of 12 month, the within group changes for these variables are expected to be greater. Expecting no change or a small change in the placebo as well as the low-dose group, our primary analyses are two subgroup comparisons: high-dose vs. low-dose and high-dose vs. placebo and the two expected between-group effect sizes (high-dose vs. low-dose and highdose vs. placebo) are large (close to the within-group effect sizes in the pilot data). With 27 participants in each group, a two-sided two sample t-test has 80% power of detecting an effect size of 0.87 (Cohen's d) at 0.025 level to maintain the overall type I error rate at 0.05 level for the two group comparisons. We will recruit 30 participants for each group to allow

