 - c. Providing on-going information to the study sponsor and the IRB: PI, Study Coordinator
 - d. Maintaining participant's research records: PI, Study Coordinator
 - e. Completing physical examination: PI, CTSU Nurse
 - f. Taking vital signs, height, weight: CTSU Nurses
 - g. Drawing / collecting laboratory specimens: CTSU Nurses
 - Performing / conducting tests, procedures, interventions, questionnaires: PI,
 Study Coordinator
 - i. Completing study data forms: Study Coordinator
 - j. Managing study database: PI

K. Assessment of Subject Safety and Development of a Data and Safety Monitoring Plan

- **a. Key personnel:** [name], [name], [name], [name], study physician at KUMC and [name], study physician at ECU.
- b. Plan for safety monitoring and review: [name] will serve as the Chair of the Data Safety Monitoring Board and will convene every 6 months with the other members, Drs. [name] and [name] to make decisions on safety of the participants. Enrollment data will also be reviewed twice a year by the DSMB. In addition, data will be reviewed on a yearly basis with the biostatistician, [name] to determine if the studies should be shortened do to either no measured effect or due to effects that are greater than what power calculations indicated. If problems occur with participants, blinded study staff will alert [name]. [name] will have access to dose and type of statin and will consult the study physicians/cardiologist to make a decision on whether the subject should be removed from the study for safety concerns. The PI and other key personnel will be examining research data on a subject to subject basis to ensure it is accurate and to address any potential problems that may arise with the protocols. In addition, Drs. [name] and [name] will discuss data at least once per month through in person meetings or by phone to ensure that data collection is occurring in a consistent manner at both locations.
- **c. Plan for adverse event reporting:** Adverse events will be defined as any untoward medical occurrence in study participants or others immediately involved in the

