injury. In spite of all safety measures, you might develop medical problems from participating in this study. You must report any suspected illness or injury to the study coordinator immediately. If such problems occur, you will be provided with emergency medical treatment and the investigator will assist you in getting proper follow-up medical treatment. Neither the investigator nor the sponsor will provide compensation for research-related injuries. Payment of lost wages, disability or discomfort is not available. You do not give up any of your rights by signing this form."

IV. Data Collection and Protection

- A. Data Management and Security: All identifiable files, data, and tissue will be coded and stored in secure locations. These data include: study progression, subject numbers, percent completion, data quality, subject retention, adverse events, etc. The PIs at both KUMC and ECU will be responsible for the quality of the data and will supervise the data acquisition with the help of study coordinators. All data will be coded for confidentiality, and only the PI, study coordinator, and study statistician will have access to the code. The results of each test on each subject will be screened by the study coordinator prior to entering on the spreadsheet. This is standard practice in our laboratories. Hard copies are kept in dedicated locked cabinets. Specific coded subject files will be sent to the study statistician for statistical analyses. These analyses will be sent to the PI and study coordinator for dissemination to appropriate co-Is. At the end of participation in the study, each subject will receive a personal data summary of their test results. The study coordinator or a study investigator will discuss the results with the subject. After 1 year, the PI's including the biostatistician, [name] will be un-blinded but the study staff will remain blinded, so that the important research findings can begin to be delineated. This will also allow for [name] to being to examine if the trial is finding more or less significant effects for outcome measures.
- **B. Sample / Specimen Collection:** All participants will be assigned a data code. Blood and tissue samples will be labeled with the participant's data code and stored in a locked freezer. Blood and tissue samples will be stored indefinitely following completion of current project for future research.

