- **C. Tissue Banking Considerations:** Following completion of the current project, remaining blood and tissue samples will remain in locked freezer indefinitely. Samples will only be used by investigators of the current project, both KUMC and ECU, when a new biomarkers or techniques of interest emerge.
- **D. Procedures to protect subject confidentiality**: Risks to confidentiality are reduced by assigning all participants to a data code. Folders are stored in locked file cabinets, and only the PI and study coordinator have access to the locked files. Individual names or initials are not used in any discussions or publications of the data.
- **E. Quality Assurance / Monitoring:** Data will be reviewed twice a year by the Board Chair. In addition, data will be reviewed on a yearly basis with the biostatistician, [name] to determine if the studies should be shortened do to either no measured effect or due to effects that are greater than what power calculations indicated. The PI and other key

personnel will be examining research data on a subject to subject basis to ensure it is accurate and to address any potential problems that may arise with the protocols. In addition, Drs. [name] and [name] will discuss data at least once per month through in person meetings or by phone to ensure that data collection is occurring in a consistent manner at both locations.

V. Data Analysis and Reporting

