- B. Expected Outcomes: Atorvastatin therapy will induce a progressive decline in skeletal muscle mitochondrial respiratory capacity that will be evident both in vivo (i.e., whole muscle NIRS) and in situ (i.e., respirometry in permeabilized fiber bundles). Based on the rationale outlined above and our preliminary data, we anticipate mitochondrial function will decline in a dose x time-dependent manner, occurring sooner in the high- verses low- dose treatment group. We further predict that the effect will be inversely related to the initial mitochondrial respiratory capacity of the skeletal muscle. Loss of mitochondrial functional capacity/content is predicted to, in turn, compromise the ability to maintain cellular redox homeostasis. Based on our previous findings (61), a shift to a more oxidized cellular redox state in skeletal muscle is expected to negatively impact insulin action. We also anticipate mitochondrial Ca2+ retention capacity will be reduced by statin therapy, providing a potential mechanism for the loss of mitochondrial content over time. If this occurs, follow up measures of genes and proteins controlling Ca2+ retention capacity (mitochondrial calcium uniporter and antiporter), and apoptosis and mitophagy (Bcl-2 (anti-apoptotic)/Bax (proapoptotic) will be performed to determine if these pathways are altered by low or high dose statins. Consistent with the reductions in mitochondrial function, we expect whole body insulin sensitivity and cardiorespiratory fitness (VO2 max) to also be reduced in a dose and time dependent manner (i.e., downstream of declines in mitochondrial function) in response to statin therapy. Of particular interest will be to determine whether reductions in mitochondrial respiratory capacity are associated with lower pain threshold and higher CK levels at rest and/or in response to exercise testing, and whether such changes are associated with compromised indices of cardiovascular function (increased heart rate and/or

reduced stroke volume), potentially occurring secondary to mitochondrial dysfunction in skeletal muscle or in another cell type like endothelial cells. Most of the data, since it is collected in real-time, will be analyzed as the study progresses allowing us to stop the study early should statistical differences in the primary outcome measures be detected prior to completion.

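### The plan's triggers for stopping or shortening the study on effect or lack of effect are not tied to month-12 data, and follow-up of those already randomised is not stated

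*Combined protocol and SAP*

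**What the plan says.** Section I.C gives the goal as finding out whether atorvastatin causes a progressive decline "that is dose and duration dependent". Section II.B describes a one-year study with at most 60 randomised and a target of 45 completers, 15 per group. Section II.C sizes the trial on the group difference "at 12 months posttreatment". Section V.A has measurements at 0, 1, 6 and 12 months.

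Two kinds of early decision are allowed:

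- **Yearly review (II.K.b, repeated in IV.E).** This involves the biostatistician, and its purpose is "to determine if the studies should be shortened do to either no measured effect or due to effects that are greater"; the yardstick is the effect assumed for the sample size. It covers both directions.
- **Running analysis (V.B).** Results are examined while data accrue, and the reason given is "allowing us to stop the study early should statistical differences in the primary outcome measures be detected prior to completion". This covers a difference only and is not tied to the yearly review.

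Section IV.A adds that after one year the principal investigators and the biostatistician "will be un-blinded but the study staff will remain blinded", partly to see how strong the effects are.

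The plan gives no boundary, no criterion for lack of effect, no deciding time point and no minimum amount of month-12 data. It does not define stopping or shortening, and does not say whether people already randomised continue to month 12. The accrual period and the start of the yearly clock are also not stated.

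**The concern.** The triggers run on calendar time or on any significant result, while the question is set at month 12.

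- **Stopping for a difference.** The 56-day pilot effect on the primary outcome was large (d = -1.48, II.C), so a difference could well show at month 1 or month 6. Stopping then could forgo the powered 12-month contrast and the 6-to-12-month segment, which is needed to tell an early one-off drop from continuing decline and which the pilot could not supply.
- **Shortening for lack of effect.** Section V.B expects decline to come sooner at the high dose than at the low dose. A null judged on months 1 and 6 may come before a slower effect has developed.

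This is separate from the type I error of repeated looks. A boundary that controls alpha could still be crossed on early biopsies, and it would not govern a decision based on lack of effect.

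**Working it through.** **1. The plan's own figure.** Section II.C: two-sample t-test, two-sided 0.025, d = 0.87, 80% power. By the noncentral t, 26 per group gives 79.3% and 27 gives 81.0%, so the stated 27 reproduces. Allowing for 10% dropout, 27/0.9 = 30.

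**2. Inputs for timing.** N = 60 and 45 completers (II.B), so the loss is 1 - 45/60 = 25%. Assumptions that the plan does not supply: uniform accrual over A years, with A varied from 1 to 5, and reviews at whole years L from first randomisation.

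**3. Formulas.**

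- Randomised by review L: 60 × min(L, A)/A
- Able to have reached month 12: 60 × min(L - 1, A)/A
- Share of those randomised who are short of month 12: 1 - min(L - 1, A)/min(L, A)
- Month-12 values per arm: (number reached/3) × 0.75

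**4. Review 1.** L - 1 = 0, so the share short of month 12 is 100% for every A. Only month-1 and month-6 data could inform a decision.

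**5. Review 2.** Power is by noncentral t at two-sided 0.025, for two effect sizes from II.C. These are 0.87, used for the sample size and equal to the NIRS pilot effect (19.07/21.80), and 1.48, the pilot effect for JO2, the primary outcome (88.5/59.9).

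| A (years) | Randomised | Reached month 12 | Share short | Per arm after loss | Power, d = 0.87 | Power, d = 1.48 |
|---|---|---|---|---|---|---|
| 1 | 60 | 60 | 0% | 15 | 0.514 | 0.948 |
| 1.5 | 60 | 40 | 33% | 10 | 0.333 | 0.798 |
| 2 | 60 | 30 | 50% | 7.5 | 0.237 | 0.635 |
| 3 | 40 | 20 | 50% | 5 | 0.142 | 0.396 |
| 4 | 30 | 15 | 50% | 3.75 | 0.098 | 0.256 |
| 5 | 24 | 12 | 50% | 3 | 0.073 | 0.173 |

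**6. Later reviews, share short of month 12.**

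- Review 3: 0% for A of 1 to 2 years, 33% for 3 to 5 years.
- Review 4: 0% for A of 1 to 3 years, 25% for 4 to 5 years.
- Review 5: 0% for A of 1 to 4 years, 20% for 5 years.

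**7. Sensitivity to N.** Section II.C plans 30 per group with 10% loss, which conflicts with II.B. The shares above do not depend on N. The per-arm numbers would be multiplied by 27/15 = 1.8.

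**8. A minimum for a null decision.** Half of the 45 planned completers is about 23 month-12 biopsies, or 23/3 = 7.7 per arm. Power for d = 0.87 is then about 24%, so non-significance at that point says little.

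**The case against.** **Stopping and shortening are undefined.** A reader might infer that the plan intends to cut off follow-up. The text does not say so. In II.K.b the sentence comes just after the DSMB's review of enrolment data, and shortening could mean closing recruitment only. This stands: truncation is permitted by the wording, not planned by it.

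**The share short of month 12 depends on accrual.** A reader might infer that a third or more are always short. Only the first-review figure holds for every accrual period, and even that assumes the clock starts at first randomisation. With accrual of one year or less, everyone could have reached month 12 by review 2.

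**The t-test is not the planned analysis.** Sections II.C and V.A specify a mixed model using all visits, with baseline and age as covariates, and II.C expects it to be more powerful. The result also depends heavily on d: at 5 per arm, power is 14% at 0.87 and 40% at 1.48. A reader might take one minus power as the rate of false null decisions. The plan nowhere equates lack of effect with non-significance, so that step is not supported.

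**An early high-dose effect should be visible by month 6.** The pilot saw respiration fall to about half within 56 days (I.C), and the primary comparisons in II.C are high dose against low dose and against placebo. This weakens the worry about a false null at high dose. It also means that duration dependence would not go wholly unanswered, because the month-1 and month-6 data would remain. It does not protect the 12-month contrast, and it makes an early stop for a difference more likely.

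**Conclusion.** The concern holds as a gap in the decision rules. As written, the plan lets the study be stopped or shortened on statistical grounds without any month-12 data, although its sample size and its question about progressive decline rest on month 12.

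Counting from first randomisation, essentially nobody has month-12 data at the first yearly review. After that the share of those randomised who are short is 0% to 50% at review 2, 0% to 33% at review 3, 0% to 25% at review 4 and 0% to 20% at review 5, for assumed accrual of 1 to 5 years. With 60 randomised, 25% loss and accrual of 1.5 to 5 years, the review-2 contrast at month 12 would rest on about 10 down to 3 per arm. A simple t-test then has 33% down to 7% power for d = 0.87 and 80% down to 17% for d = 1.48. These powers are illustrative, since the mixed model may do better.

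The documents do not support saying that follow-up will be cut off, that a fixed fraction will be lost, or that a null reading would be false at any particular rate.

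**What to change.** Put the same text in II.K.b, IV.E and V.B:

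1. Any decision based on effect or on lack of effect uses the month-12 contrast, and is taken only once a pre-stated minimum number of month-12 biopsies exists. The number should be justified by its operating characteristics under the planned mixed model. Non-significance alone at small numbers is not grounds for stopping for lack of effect.
2. A statistical decision to stop or shorten closes enrolment. Participants already randomised are still offered their planned month-6 and month-12 assessments, and enter one final primary analysis after the last of these.

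The accrual period and the start of the yearly clock should also be stated.

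Safety decisions, and whether participants remain on study drug after a statistical stop, are for the DSMB and the study physicians. The sections should be reconciled on this point, because it determines what a later month-12 biopsy measures.

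The cost is a few sentences in three places. A statistical stop would save less time, by up to 12 months of visits already planned. At review 2 that concerns 12 to 30 people for accrual of 1.5 to 5 years (randomised minus reached in the table). No extra participants or procedures are needed.
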